8.2.7. Time to First BILAG A Flare

A BILAG A flare is defined as at least 1 new BILAG A organ domain score compared to baseline. Time to the first BILAG A flare will be summarised as per the BILAG 1A/2B flare endpoint (see Section 8.2.6).

8.2.8. Time to First Renal Flare

Only time to first renal flare will be analysed. Although a renal flare rate was of interest at the time of the protocol design writing, renal flare rates have been relatively

uncommon, and do not provide much clinical value at this current time. Focus will be placed upon providing a summary of the first renal flare event.

Assessments every 6 months during BEL114333 will not allow the use of the same definition of renal flares as in the parent studies, which requires assessments to be performed at two or more consecutive monthly visits. Thus, a renal flare is defined as the occurrence of one or more of the following criteria at a single (belimumab) visit at every Week 24 and Week 48, timepoints at which both protein creatinine ratio and lab assessments are scheduled in the protocol. Note, when identifying renal flares, data within the visit window at Week 24 and Week 48 visits will be considered.

- 1. An increase in 24-hour urine protein equivalent levels to
 - a. > 1 g if the baseline value was < 0.2 g,
 - b. > 2 g if the baseline value was 0.2 to 1 g, or
 - c. More than twice the value at the baseline if the baseline value is > 1 g.
- 2. An increase in serum creatinine of >20 % or an increase of at least 0.3 mg/dL, accompanied by at least one of proteinuria (>1 g/24 hour equivalent), hematuria (≥ 4 red blood cells [RBCs]/high-power field [hpf]), cellular (RBC or WBC) casts. The inclusion of 'at least one of' and 'RBC or WBC' casts is an addition to the protocol specified definition. This addition has been included in the parent study BEL113750 RAP.
- 3. Treatment-emergent, hematuria (≥ 11 to 20 RBCs/hpf) or an increase in hematuria by 2 grade compared with baseline, associated with > 25% dysmorphic RBCs, glomerular in origin, exclusive of menses, accompanied by either an 0.8 g increase in 24-hour urinary protein levels (equivalent) or new RBC casts [Alarcón-Segovia, 2003].

To clarify criterion 2, [an increase in serum creatinine of > 20% OR an increase of at least 0.3 mg/dL], AND [proteinuria (> 1 g/24-hour equivalent) OR hematuria (≥ 4 red blood cells {RBCs}/high-power field {hpf}) OR cellular (RBC or WBC) casts].

To clarify criterion 3, [treatment-emergent, hematuria (≥ 11 to 20 RBCs/ hpf) OR (an increase in hematuria by 2 grades compared with baseline AND > 25% dysmorphic RBCs, glomerular in origin, exclusive of menses)], AND [0.8 g increase in 24-hour urinary protein levels (equivalent) OR new RBC casts].

Time to first renal flare is calculated as the number of days from first dose of belimumab treatment up to the first renal flare event (event date - first belimumab dose date + 1). The event date is defined by the scheduled laboratory assessment date. The disposition of subjects is defined as follows:

Subject Disposition	Event Met	Event Date
Subject has a renal flare		
Subject has a renal flare during the study	Yes	Date of first renal flare

Subject does not have a renal flare										
Subject withdraws from the study	No	Censored at last available date where all relevant parameters were assessed.								
Subject dies during the study	No	Censored at date of death.								
Subject completes the study *	No	Censored at last available date where all relevant parameters were assessed.								

^{*}As per the protocol. Includes subjects who transferred to study BEL116027, or who were still participating in the study at the time of the sponsor decision to close/terminate the study

Analyses for the first renal flare will use the same methodology as for severe SFI flares (see Section 8.1.6).

8.2.9. Proteinuria Percent Change from Baseline

Because no subjects had an actual 24 hour urine collection to assess proteinuria, the definition of proteinuria can be simplified to just using the spot urine PC ratio to assess the degree of proteinuria present at Week 24 and Week 48 (in every year). Proteinuria will be defined as a urine PC ratio > 0.5 mg/mg. Note, the PC ratio reported in mg/mg is the 24 hour gram equivalent.

For subjects with proteinuria at baseline, the absolute value and percent change from baseline in urine PC ratio will be summarised using descriptive statistics, and presented by the parent randomised treatment group and overall, for each belimumab visit.

For this group of subjects having proteinuria at baseline, the data will be displayed graphically using a line graph. The plot will show the mean percent change from baseline (\pm SE) over time.

See Section 11.5.4.6 for the conversion of urine PC ratio from SI units to mg/mg.

8.2.10. Proteinuria shifts

Proteinuria shifts as measured by spot urine PC ratio.

Urine PC ratio values will be summarised according to the following categories at baseline: normal ($\leq 0.5 \text{ mg/mg}$) or high (> 0.5 mg/mg).

For each Week 24 and Week 48 belimumab visit (in every year), the data will be summarised by baseline status defined as normal or high.

- For subject with a normal value at baseline, the shift categories at the specified visit are shown as either 'No change' or 'Normal to High'.
- For subjects with a high value at baseline, the shift categories at the specified visit are shown as either 'No Change' or 'High to Normal'.

Additionally, the spot urine PC ratio values will be summarised based on shifts occurring any time while on treatment.

- For subject with a normal value at baseline, the number (%) of subjects with at least one high post-baseline value will be presented as 'Normal to High'; otherwise as 'No Change'.
- For subjects with a high value at baseline, the number (%) of subjects with at least one normal post-baseline value will be presented as 'High to Normal'; otherwise as 'No Change'.

8.2.11. Prednisone Percent Change from Baseline

The observed values and percent change from baseline in average daily prednisone dose will be summarised using descriptive statistics, and presented by the parent randomised treatment group and the total Safety population, for each Week 24 and 48 belimumab visit (in every year).

The derivation of average daily prednisone dose and conversion to the prednisone-equivalent dose are provided in Section 11.5.3

Total Safety population data will be displayed graphically using a line graph. The plot will show the mean percent change from baseline (\pm SE) over time.

8.2.12. Prednisone Dose ≤ 7.5 mg/day for Subjects with an Average Daily Dose > 7.5 mg/day at Baseline

For subjects with an average daily prednisone dose > 7.5 mg/day at baseline, the proportion of subjects with an average daily prednisone dose reduced to ≤ 7.5 mg/day will be summarised, and presented by the parent randomised treatment group, and overall, for each Week 24 and Week 48 belimumab visit (in every year).

For this group of subjects having an average daily prednisone dose > 7.5 mg/day at baseline, the data showing reduction to ≤ 7.5 mg/day will be displayed graphically using a line graph. The plot will show the proportion of subjects with this reduction (\pm SE) over time.

8.2.13. Prednisone Dose > 7.5 mg/day for Subjects with an Average Daily Dose ≤ 7.5 mg/day at Baseline

For subjects with an average daily dose ≤ 7.5 mg/day at baseline, the proportion of subjects with an average daily prednisone dose increased to > 7.5 mg/day, will be summarised, and presented by the parent randomised treatment group, and the overall, for each Week 24 and Week 48 belimumab visit (in every year).

For this group of subjects having an average daily prednisone dose \leq 7.5 mg/day at baseline, the data showing elevation to > 7.5 mg/day will be displayed graphically using a line graph. The plot will show the proportion of subjects with this increase (\pm SE) over time.

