8. DATA ANALYSIS AND STATISTICAL CONSIDERATIONS

There is no statistical sample size calculation. All analyses will be performed using descriptive statistics and will be exploratory in nature. The data base will be locked once all subjects have completed the Week 16 follow-up visit. Immunogenicity and B cell marker data collected at the 6-month post-treatment visit will be reported separately as an addendum to the clinical study report. Details of the analysis will be given in the Reporting and Analysis Plan (RAP).

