2.4. Statistical Hypotheses

Since this is an open-label continuation, no formal statistical hypothesis testing will be performed. Any comparisons between the parent study randomised treatment groups will be purely descriptive.

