- Due to the additional 6 month OL extension for SC subjects entering BEL114333, there is a 6 month off-set in the data capture between the parent studies. As a result, for SLICC, immunoglobulins and B cell subsets, captured on an annual basis in BEL114333, the data captured at each analysis visit stratifies by parent study. As such these endpoints will be tabulated by parent study, and the data will not be aggregated.
- Summaries by belimumab Treatment: Data will be mapped to the year by windowing starting at the time of first belimumab treatment.

The GlaxoSmithKline group of companies

BEL114333

- Listings: If endpoints reported, data will be presented in listings as required.
- Figures: error bars will be displayed.

Unless otherwise stated, no imputation for missing values will be conducted.

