9.1.1. Percent change from baseline

The absolute values and percent change from baseline in immunoglobulins, autoantibodies (anti-dsDNA), complement levels (C3 and C4), and B cell subsets (see Section 11.5.5.1) will be summarised using descriptive statistics, and presented by the parent randomised treatment group and the total Safety population. The frequency of these lab specimens vary and thus will be shown in accordance their respective timings (see Section 11.1).

Total Safety population data will be displayed graphically using a line graph. The plot will show the median percent change from baseline (interquartile range bars) over time.

Note: For immunoglobulins and B cell subsets, the data will be presented separately for subjects from each parent study.

Additionally, for anti-dsDNA, analyses will be performed among subjects who were positive at baseline; for complement levels, analyses will be performed among subjects with low values at baseline. See Section 11.5.5 for baseline classifications.

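### SAP Figures 3.15 and 3.16 use ± SE bars that shrink to nothing at 0% or 100%, and Figure 3.13 uses a mean percent change that understates a fall in proteinuria

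*SAP*

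**What the plan says.** SAP 8.2.12 follows subjects above 7.5 mg/day of prednisone at baseline and plots the share at or below that dose at each Week 24 and Week 48 visit: "The plot will show the proportion of subjects with this reduction", with ± SE (Figure 3.15). SAP 8.2.13 does the reverse for subjects at or below 7.5 mg/day: "The plot will show the proportion of subjects with this increase", again ± SE (Figure 3.16). No formula for the SE, interval method or minimum n is given.

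For proteinuria, SAP 8.2.9 limits the analysis to subjects with the condition at baseline ("Proteinuria will be defined as a urine PC ratio > 0.5 mg/mg"). For Figure 3.13 it says "The plot will show the mean percent change from baseline", with ± SE. SAP 11.4.2.4 defines percent change as 100 × (visit value − baseline)/baseline.

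For immunoglobulins, anti-dsDNA, complement and B cell subsets, SAP 9.1.1 takes a different course: "The plot will show the median percent change from baseline (interquartile range bars) over time".

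The general rule in SAP 5.1 is only "Figures: error bars will be displayed", with no type stated. The protocol says "There is no statistical sample size calculation" (Section 8), and SAP 2.4 says "no formal statistical hypothesis testing will be performed".

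**The concern.** Error bars tell the reader how far to trust each point. A binomial SE estimated from the observed proportion is zero at 0/n and n/n, so the bar disappears just when a small group happens to be unanimous. The point then looks exact.

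The plan itself implies small groups late on:
- Efficacy is summarised as observed cases, so n falls with dropout (SAP 11.6.2.2).
- Few subjects are expected beyond six years (SAP 11.2.1), and the last year of data covers one parent group only (SAP 5.1).
- The visit map in SAP 11.2.2 has no visits beyond Year 5 for subjects from BEL112341.
- Each prednisone figure uses only a subset of whoever remains.

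For proteinuria, percent change is asymmetric: a halving counts −50 and a doubling counts +100. A few large rises can outweigh many real falls in the mean. At stake is a correct reading of three descriptive figures, not any test or decision.

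**Working it through.** The plan has no figure of its own to reproduce. The documents give neither the subset sizes nor the spread of the protein:creatinine ratio, so every n, p and log-SD below is an assumption.

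**1. Proportions (Figures 3.15 and 3.16).** SE = sqrt(p(1−p)/n). At p = 0 or p = 1 this is sqrt(0/n) = 0 for every n. A 95% interval built as p ± 1.96 × SE collapses in the same way.

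| Observed | ± SE bar | Wilson 95% | Clopper-Pearson 95% |
|---|---|---|---|
| 0/5 | 0 to 0 | 0 to 43.5% | 0 to 52.2% |
| 0/10 | 0 to 0 | 0 to 27.8% | 0 to 30.8% |
| 10/10 | 100 to 100% | 72.2 to 100% | 69.2 to 100% |
| 0/25 | 0 to 0 | 0 to 13.3% | 0 to 13.7% |
| 0/50 | 0 to 0 | 0 to 7.1% | 0 to 7.1% |

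How often this happens depends on n and the true proportion. The chance that all n subjects meet the criterion is p^n:
- n = 10, p = 0.9: 0.9^10 = 35%.
- n = 10, p = 0.7: 0.7^10 = 3%.
- n = 25, p = 0.9: 0.9^25 = 7%.

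The same probabilities apply at the 0% end with p replaced by 1 − p.

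Coverage of ± 1 SE, nominally 68%, at n = 10 and p = 0.9: only the bars for 8/10 (67.4 to 92.6%) and 9/10 (80.5 to 99.5%) contain 90%. Coverage is 0.194 + 0.387 = 58%. At n = 5 it is 33%, and at n = 25 it is 63%.

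**2. Proteinuria (Figure 3.13).** Suppose the ratio of visit value to baseline is lognormal with median m and log-SD s. The expected mean percent change is 100 × (m × exp(s²/2) − 1). For a 30% median fall, m = 0.7:
- s = 0.5: 0.7 × 1.133 = 0.793, or −21%.
- s = 0.7: 0.7 × 1.278 = 0.894, or −11%.
- s = 1.0: 0.7 × 1.649 = 1.154, or +15%.

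The sign changes at s = sqrt(−2 ln 0.7) = 0.845. For other falls the threshold is 0.46 (10% fall), 0.67 (20%), 1.01 (40%) and 1.18 (50%).

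In 100,000 simulated samples of n = 10 with a 30% fall, the plotted mean was above zero while the sample median was below zero in 5% of samples at s = 0.5, 27% at s = 0.8 and 39% at s = 1.0.

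**3. One outlier (invented data).** Ten subjects all start above 0.5 mg/mg. Five fall by 50%, four fall by 60%, and one rises from 0.7 to 4.9 mg/mg (+600%). The mean is (5 × −50 + 4 × −60 + 600)/10 = +11%, with SE 65.5. The median is −50%, with quartiles −60% and −50%. The group mean ratio falls from 1.73 to about 1.20 mg/mg.

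**The case against.** The study is descriptive, safety is its primary objective, and these three figures belong to the other efficacy endpoints. Tables 3.25, 3.28 and 3.29 report the same data by visit, and the default statistics in SAP 5.1 include n, median and quartiles, or counts and percentages. Table 3.26 adds proteinuria shifts between normal and high, which one outlier cannot reverse. Mean ± SE is also the style of neighbouring efficacy figures (8.2.1, 8.2.3, 8.2.11). The restriction to baseline ratios above 0.5 mg/mg removes the tiny denominators that inflate percent change most. A ± SE bar makes no confidence claim, and the mean and median are different summaries. All of this stands and limits the harm. It does not give a zero-length bar any meaning, nor explain why percent change is plotted as a mean here and as a median in 9.1.1.

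A reader might go further in four ways that the documents do not support:
- *All responder figures use SE.* For Figures 3.1 to 3.4 the text says only that a line graph is drawn, and 5.1 leaves the bar type open. They share a shell code with 3.15 and 3.16, which makes SE plausible, but the shells are in a separate document.
- *Every other laboratory marker is shown as a median.* SAP 9.1.1 covers four marker groups. The safety laboratory graphs in 7.4.2 name no statistic.
- *The figures are the main efficacy display.* SAP 2.1 has efficacy tabulated by parent treatment group, with graphs for the total population only.
- *Figure 3.13 will show a fall as a rise.* That needs wide spread or an outlier, and neither is established.

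**Conclusion.** The point holds for Figures 3.13, 3.15 and 3.16 and is worth acting on, with modest impact. The zero-length bar follows from the formula at any n, provided the usual binomial SE is meant. How often it appears depends on subset sizes and proportions that the documents do not state: 35% of samples at n = 10 and a true 90%, but 3% at a true 70%.

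For proteinuria, the mean lies above the median under any lognormal spread, so a fall is understated. For a 30% fall the expected mean turns positive only when the log-SD exceeds about 0.85. Understatement is therefore the general conclusion, and reversal is only a possibility. No inference or decision rests on these figures, and the companion tables allow a careful reader to recover the correct picture.

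**What to change.** - **Figures 3.15 and 3.16:** replace ± SE with Wilson or Clopper-Pearson 95% intervals, name the method in 8.2.12 and 8.2.13, and show n under each visit.
- **Figures 3.1 to 3.4:** state what the error bars are. If they are SEs, make the same change.
- **Figure 3.13:** plot median percent change with interquartile bars, as 9.1.1 already does for the biomarkers.

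The cost is a few lines of SAP text and plotting options. No data, endpoint or population changes. The drawback is wider bars at late visits. The proportion figures would then carry 95% intervals while neighbouring mean plots keep ± SE, so each figure needs a footnote naming its bar.

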9. BIOMARKER ANALYSES

The biomarker parameters will be based on the Safety population, unless otherwise specified.

9.1. Overview of Planned Biomarker Analyses

Table 14 provides an overview of the planned biomarker analyses, with further details of data displays being presented in Appendix 12: List of Data Displays.

Table 14 Overview of Planned Biomarker Analyses

Endpoint	Sum	Summary				
	Т	F	L			
Serum Immunoglobulin (IgG, IgM & IgA)						
Lab Parameter Visit Values	Υ [1] [4]					
Lab Parameter % Change from BL	Υ [1] [4]	Y				
IgA, IgG, IgM below LLN by Visit	Υ [4]					
IgA, IgG, IgM below LLN by Year Interval	Υ					
Autoantibodies (anti-dsDNA)						
Lab Parameter Visit Values	Υ [1]		Υ [2]			
Lab Parameter % Change from BL	Υ [1]	Υ				
Lab Parameter Visit Values for Subjects Positive at BL	Υ [1]					
Lab Parameter % Change from BL for Subjects Positive at BL	Υ [1]	Υ				
Complement (C3, C4) Levels						
Lab Parameter Visit Values	Υ [1]		Υ [2]			
Lab Parameter % Change from BL	Υ [1]	Υ				
Lab Parameter Visit Values for Subjects with Low Complement at BL	Υ [1]					
Lab Parameter % Change from BL for Subjects with Low Complement at BL	Y [1]	Υ				
B Cell Subsets [3]						
Lab Parameter Visit Values	Υ [1] [4]		Y			
Lab Parameter % Change from BL	Υ [1] [4]	Υ				

NOTES:

- BL = Baseline, T = Table, F = Figure, L = Listing, Y = Yes display generated, (xN) = Number of separate displays
 generated
- Summary = Represents TFL related to any summaries (i.e. descriptive statistics) of the observed raw data.
- Individual = Represents FL related to any displays of individual subject observed raw data.
- [1] A combined display will be generated for observed and change from baseline for each parameter.
- [2] Combined into a single display.
- [3] B cell data are collected only at 'selected sites' in which the selected sites were all Japan sites. See Section 11.5.5.1 for additional information.
- [4] Data summarised separately by parent study. See Section 5.1.

9.1.1. Percent change from baseline

The absolute values and percent change from baseline in immunoglobulins, autoantibodies (anti-dsDNA), complement levels (C3 and C4), and B cell subsets (see Section 11.5.5.1) will be summarised using descriptive statistics, and presented by the parent randomised treatment group and the total Safety population. The frequency of these lab specimens vary and thus will be shown in accordance their respective timings (see Section 11.1).

Total Safety population data will be displayed graphically using a line graph. The plot will show the median percent change from baseline (interquartile range bars) over time.

Note: For immunoglobulins and B cell subsets, the data will be presented separately for subjects from each parent study.

Additionally, for anti-dsDNA, analyses will be performed among subjects who were positive at baseline; for complement levels, analyses will be performed among subjects with low values at baseline. See Section 11.5.5 for baseline classifications.

9.1.2. Immunoglobulin (IgG, IgA and IgM) below LLN

The number (%) of subjects with immunoglobulin (IgG, IgA and IgM) values below the lower limit of normal (LLN) will be summarised by the parent randomised treatment group, for each belimumab visit. This data will be presented separately for subjects from each parent study. See Section 11.5.5 for LLN classifications.

Additionally, the immunoglobulin data for all subjects will be shown by year interval and at "any time post-baseline". See Section 11.5.5 for LLN classifications.

11. APPENDICES

Section	Appendix
RAP Section 5	: General Considerations for Data Analyses & Data Handling Conventions
Section 11.1	Appendix 1: Time & Events
Section 11.2	Appendix 2: Assessment Windows
Section 11.3	Appendix 3: Adverse Event Collapsing Rules and Assignment of Adverse Events to Study Year
Section 11.4	Appendix 4: Data Display Standards & Handling Conventions
	Study Treatment & Sub-group Display Descriptors
	Baseline Definitions & Derivations
	Reporting process & Standards
Section 11.5	Appendix 5: Derived and Transformed Data
	General, Study Population & Safety
	Efficacy
	Biomarkers
Section 11.6	Appendix 6: Premature Withdrawals & Handling of Missing Data
	Premature Withdrawals and Completion
	Handling of Missing Data
Section 11.7	Appendix 7: Methods for Handling Centres
Section 11.8	Appendix 8: Examination of Covariates, Subgroups & Other Strata
Section 11.9	Appendix 9: Laboratory Parameters & Adverse Events Grading Tables
Section 11.10	Appendix 10: PSAP Sections for AESI Reporting.
Other RAP App	endices
Section 11.11	Appendix 11: Abbreviations & Trade Marks
Section 11.12	Appendix 12: List of Data Displays

11.1. Appendix 1: Time & Events

11.1.1. BEL114333 Protocol Defined Time & Events

11.1.1.1. Open-label Year 1

Study Visit	Wk 48 of BEL 113750/ On/before Day 168 of C11151	Wk 0 (Wk 52 of BEL11375 0/Day 168 of C1115) +1 week ¹	Wk 4	Wk 8	Wk 12	Wk 16	Wk 20	Wk 24	Wk 28	Wk 32	Wk 36	Wk 40	Wk 44	Wk 48	EXIT ²	16 wk FU ± 7d post infusion	6 month FU ± 7d post infusion
Study Day		Day 0	28 ±7d	56 ±7d	84 ±7d	112 ± 7d	140 ±7d	168 ±7d	196 ±7d	224 ±7d	252 ±7d	280 ±7d	308 ±7d	336 ±7d			
Written Informed Consent	Х																
Inclusion/Exclusion Criteria		X*															
Efficacy Assessments																	
Disease Activity Scales: SELENA SLEDAI, SLE Flare Index, BILAG and PGA ³		Х						x						Х	х		
SLICC/ACR Damage Index		Х												Х	Х		
Safety Assessments																	
Symptom-driven Physical Exam		X						Х						Х	Х	Х	
Record Concurrent Medications		Х	Х	Х	Х	Х	Х	Х	Χ	Х	Х	Х	Х	Х	Х	Х	
Assess/Record Adverse Events ⁴		Х	Х	Х	Х	Х	Х	Х	Χ	Х	Х	Х	Χ	Х	Х	Х	
Vital Signs 5, 11		Χ	Χ	Χ	Χ	Χ	Χ	Χ	Χ	Χ	Χ	Χ	Χ	Χ	Χ	Х	

Study Visit	Wk 48 of BEL 113750/ On/before Day 168 of C11151	Wk 0 (Wk 52 of BEL11375 0/Day 168 of C1115) +1 week ¹ Day 0	Wk 4	Wk 8	Wk 12	Wk 16	Wk 20	Wk 24	Wk 28	Wk 32	Wk 36	Wk 40	Wk 44	Wk 48	EXIT ²	16 wk FU ± 7d post infusion	6 month FU ± 7d post infusion
Study Day			±7d	±7d	±7d	$\pm 7d$	±7d										
Laboratory Assessments																	
Labs: Haematology & Modified Chem 20 (non fasting) ⁵		Х	Х		х			Х			х			Х	Х	Х	
Urinalysis ⁵		Х	Χ		Χ			Χ			Χ			Х	Х	Χ	
Spot urine (protein to creatinine ratio) ^{5, 6}		Х						Х						Х	Х		
Urine Pregnancy Test 5,7		Х	Х	Х	Х	Х	Х	Х	Х	Х	Х	Χ	Χ	Х	Х	Х	
C3, C4, Anti-ds DNA Autoantibodies ⁵		Х						Х						Х	Х		
IgG ^{5, 8}		Х			Χ			Χ						Х	Х	Х	
IgA & IgM ^{5, 8}		Х												Х	Х		
PT/ PTT		X*															
Exploratory Lab Assessments																	
Immunogenicity 9		Х						Χ						Х	Х	Χ	X ^{9A}
B cell Markers 10		Χ												Х	Х		Χ
Investigational Product																	
Belimumab Administration 11, 12		Х*	Х	Х	Χ	Х	Х	Х	Х	Х	Х	Х	Х	Х			

Calendar represents a yearly (48-week) ongoing visit schedule until the subject is terminated from the study. During the first 48 weeks, the 1st visit is Baseline/Day 0. For all subsequent 48 week calendar years, the 1st visit will be Week 4. Note: BEL112341 is referred to as 'C1115' in this time and events table.

*See footnote 1.

- 1. **For subjects from BEL113750**: The Week 52 visit in the parent study Protocol BEL113750 serves as the Day 0 visit for the Protocol BEL114333. Performance of all the Week 52 procedures in BEL113750 will cover nearly all the procedures that are required for Day 0 of this protocol. Procedures necessary for both this protocol and the prior Phase III protocol need only be performed once and shall be recorded to CRFs as described in Protocol, Section 6.1. At Week 48 of BEL113750, a subject should sign the informed consent for the BEL114333 study. In addition to the Week 52 procedures for BEL113750, a subject should be reassessed for inclusion/exclusion criteria of the BEL114333 study and receive belimumab (those procedures marked with an asterisk). Subjects must be able to receive the 1st dose of belimumab (Day 0) for BEL114333 four weeks (minimum of 2 weeks, maximum of 8 weeks) after the last dose in BEL113750.
 - For subjects from C1115: The Day 168 (Week 24) visit in the open-label extension phase of C1115 serves as the Day 0 visit for the Protocol BEL114333. Performance of all the Day 168 procedures in C1115 will cover nearly all the procedures that are required for Day 0 of this protocol. Procedures necessary for both this protocol and the prior Phase III protocol need only be performed once and shall be recorded to CRFs as described in Protocol, Section 6.1. On or before the Day 168 visit, a subject should sign the informed consent for the BEL114333 study. In addition to the Day 168 procedures for C1115, a subject should be reassessed for inclusion/exclusion criteria of the BEL114333 study and receive IV belimumab. The target for starting IV belimumab (Day 0) for BEL114333 is 1 week after the last dose of SC belimumab (scheduled for Week 23 in the open-label extension). The EXIT visit of the C1115 study (Week 24) serves as the Day 0 visit for the Protocol BEL114333, and will have a +1 week visit window.
- 2. The Exit visit will occur approximately 4 weeks after the last dose of belimumab. Belimumab should not be administered, and all Exit visit assessments must be completed.
- 3. Refer to Protocol, Section 6.2.2.3 for guidelines for scoring proteinuria for SELENA SLEDAI and BILAG evaluation.
- 4. AE reports should be updated or completed prior to dosing. Ongoing Adverse events of BEL113750 have to be transferred and followed up in BEL114333.
- 5. Samples should be obtained prior to dosing.
- 6. A 24-hour urine may be done as an additional assessment if clinically indicated (e.g., renal flare).
- 7. Results of urine pregnancy test at subsequent visits, if required, must be available prior to dose. See 'Critical Baseline Assessments', Protocol, Section 6.1 for definition of those exempted from subsequent pregnancy testing.
- 8. Serum immunoglobulin isotypes: IgG, IgM, IgA.
- 9. Immunogenicity testing includes quantifying the amount of belimumab present in the samples using the belimumab PK assay.
 - ^{9A}For any subject who had an anti-belimumab antibody response at the 16-week follow-up visit (or last study visit at which immunogenicity was assessed if the 16-week follow-up immunogenicity sample is not available), an attempt will be made to obtain a serum sample for anti-belimumab antibodies at least 6 months after the last dose of study agent.
- 10. Biological Markers include FACS of peripheral lymphocytes: B lymphocytes (CD20+, CD20+/27+ memory, CD20+/27- naïve, CD20+/69+ activated, CD20+/138+ plasmacytoid, CD19+/27BRIGHT/38BRIGHT SLE subset and CD20-/138+ plasma cells). Note: B-cell subsets to be drawn at selected sites only.
- 11. It is recommended the patient be weighed at each visit prior to dosing. If weight changes by more than 5% from the Day 0 weight, the weight at the current visit should be used for calculating the dose. Systolic and diastolic blood pressure (sitting), heart rate, and oral temperature will be measured (see Protocol, Section 6.3.11).
- 12. Subjects will remain under clinical supervision for 3 hours after completion of the first 2 infusions. See Protocol, Section 5 and Protocol, Section 6.3.9.

